12.2	Monitoring and Quality Assurance.....	39
12.3	Amendments	40
12.4	Annual progress report.....	40
12.5	Temporary halt and (prematurely) end of study report.....	40
12.6	Public disclosure and publication policy.....	40
13.	STRUCTURED RISK ANALYSIS.....	42
13.1	Potential issues of concern.....	42
13.2	Synthesis	43
14.	REFERENCES	44
	Appendix 1: Stopping rules.....	45
	Appendix 2: Surgical flowcharts.....	53
	Appendix 3: CTCAE criteria.....	56
	Appendix 4: Procedures and forms data collection.	58
	Appendix 5: Participating centres	61
	Appendix 6: Questionnaires.....	62
	EQ-5D-5L	63
	Adjusted GCLQ.....	64
	Decision Conflict Scale	65
	Decision Regret Scale (DRS).....	67

LIST OF ABBREVIATIONS AND RELEVANT DEFINITIONS

ABR	ABR form, General Assessment and Registration form, is the application form that is required for submission to the accredited Ethics Committee (In Dutch, ABR = Algemene Beoordeling en Registratie)
AE	Adverse Event
AR	Adverse Reaction
CA	Competent Authority
CCMO	Central Committee on Research Involving Human Subjects; in Dutch: Centrale Commissie Mensgebonden Onderzoek
CV	Curriculum Vitae
DSMB	Data Safety Monitoring Board
EU	European Union
EudraCT	European drug regulatory affairs Clinical Trials
GCP	Good Clinical Practice
GDPR	General Data Protection Regulation; in Dutch: Algemene Verordening Gegevensbescherming (AVG)
IB	Investigator's Brochure
IC	Informed Consent
IFL	Inguinal-femoral lymph node dissection
IMP	Investigational Medicinal Product
IMPD	Investigational Medicinal Product Dossier
METC	Medical research ethics committee (MREC); in Dutch: medisch ethische toetsing commissie (METC)
(S)AE	(Serious) Adverse Event
SLN	sentinel lymph node
SPC	Summary of Product Characteristics (in Dutch: officiële productinformatie IB1-tekst)
Sponsor	The sponsor is the party that commissions the organisation or performance of the research, for example a pharmaceutical company, academic hospital, scientific organisation or investigator. A party that provides funding for a study but does not commission it is not regarded as the sponsor, but referred to as a subsidising party.
SUSAR	Suspected Unexpected Serious Adverse Reaction

- UAVG** Dutch Act on Implementation of the General Data Protection Regulation;
in Dutch: Uitvoeringswet AVG
- WMO** Medical Research Involving Human Subjects Act (in Dutch: Wet Medisch-
wetenschappelijk Onderzoek met Mensen)

SUMMARY

Rationale: Standard groin treatment in recurrent vulvar cancer consists of a uni or bilateral inguinal lymph node dissection (IFL), whereas in the primary setting a sentinel lymph node (SLN) procedure is performed in case of unifocal tumours < 4cm without suspicious groin lymph nodes at imaging. The advantages of SLN procedure over an IFL are obvious: the short and long term sequels such as wound healing problems, lymph cyst formation, recurrent erysipelas and lymph oedema are much less common after SLN procedure. In a national retrospective analysis we showed that SLN is feasible in selected recurrent vulvar cancer patients. This national prospective observational study aims to investigate the safety of such procedure.

Since little is known on the outcome of 1st recurrent vulvar cancer we also gather more information on women with a first recurrence, not eligible for the SLN procedure.

Objective: The primary objective is to investigate the safety of replacing complete IFL by the SLN procedure in patients with local recurrent vulvar squamous cell carcinoma without suspicious groin lymph nodes.

Study design: This is predominantly a prospective multicentre observational study on sentinel lymph node (SLN) procedure in women with local recurrent vulvar cancer. Besides it is an observational study on the treatment and outcome of women with a local recurrent vulvar cancer, not eligible for the SLN procedure.

Study population: Women with their first local recurrence of vulvar cancer, 18 years and older, fit for surgical treatment, who had previous groin treatment as part of the primary treatment: none, uni- or bilateral SLN procedure, or IFL and/or radiotherapy. Excluded are women with previous ipsilateral IFL and radiotherapy, or bilateral IFL and radiotherapy. Women that do not fulfil these criteria will be included in the observational arm.

Intervention: Surgical treatment consists of standard local treatment (wide local resection, vulvectomy) of the vulvar tumour combined with a uni- or bilateral SLN procedure.

Main study parameters/endpoints: Primary end point is the number of groin recurrences after SLN procedure. Secondary endpoints: success rate of the SLN procedure, surgical drawbacks, wound healing problems, long term sequela, and quality of life in women treated for a 1st recurrent vulvar cancer.

Nature and extent of the burden and risks associated with participation, benefit and group relatedness: In this study, similar to the current routine, preoperative imaging of chest, abdomen and groins is performed. The patient is informed about the standard procedure and about the option of a SLN procedure. She and her treating gynaecologist decide on the preferred treatment. Prior to surgery the planned surgical procedure is recorded, including patients' consent for IFL in case the SLN procedure fails. The surgical procedure (SLN procedure) will be less extensive compared to routine IFL, with less unfavourable short and long term effects, such as infections and lymph oedema. In case of groin metastases detected in the SLN procedure further treatment is warranted, either by surgery (uni or bilateral IFL) and/or by radiotherapy. At follow up participants will undergo (non-invasive) ultrasonography studies of the groin at 6 and 12 months. Participants will be asked to fill in additional questionnaires at baseline, 6 and 12 months. In case of a groin recurrence (due to failed SLN procedure) further treatment is warranted, probably resulting in a poorer prognosis with a high mortality rate (probably 80-90%). Currently, robust data on the occurrence of groin recurrence after either SLN biopsy or IFL for recurrent vulvar cancer is lacking. Given the lower morbidity and less short and long term side effects of the SLN procedure compared to IFL an additional 5% failure rate is considered acceptable.

1. INTRODUCTION AND RATIONALE

The treatment for vulvar cancer has changed over the last decades. Currently the standard treatment for unifocal squamous cell carcinoma (SCC) of the vulva < 4 cm diameter without suspicious inguinofemoral lymph nodes at imaging consists of wide local excision and sentinel lymph node (SLN) procedure of the inguinofemoral lymph nodes (1-4). The advantages of SLN procedure over an inguinofemoral lymphadenectomy (IFL) are obvious: the short and long term sequels such as wound healing problems, lymph cyst formation, recurrent erysipelas and lymph oedema are much less common after SLN procedure (4). Lymphedema and recurrent erysipelas were seen in respectively 1.9% and 0.4% after SLN procedure and in respectively 25.2% and 16.2% after inguinofemoral lymphadenectomy (4). Groin recurrences after negative SLN procedures in primary vulvar SCC patients were reported in 2–3% of the patients (1, 5, 6). Unfortunately, a groin recurrence after IFL have a very high mortality rate, the prognoses after a negative SLN procedure is unclear; therefore very strict criteria with respect to tumour characteristics, preoperative and pathological assessment and surgical technique should be met to guarantee the safety of the SLN procedure and to minimize the number of false negative results and the risk of groin recurrence. Local recurrences of SCC of the vulva are reported in 20–46%(7). Many of these recurrences might be second primary tumours in a background of lichen sclerosis and differentiated vulvar intraepithelial neoplasia or high grade squamous cell intraepithelial lesion (HSIL) of the vulva rather than a real recurrence(8, 9). In patients with recurrent vulvar SCC, IFL is considered standard treatment for patients who previously did not undergo an IFL(10). So, in case of a local recurrence, only after bilateral IFL groin surgery is omitted. Since many of these patients are elderly and frail an alternative treatment other than IFL may be justified to avoid or reduce long term morbidity in this particular group of patients. In a retrospective analysis of it was shown that in a considerable number of patients groin surgery is not performed, in contrast with the guideline. In a retrospective study including 200 women with a macro invasive local recurrence the risk for groin metastases was 18%, and related to depth of invasion and tumour diameter. (Personal communication [name]¹). The lower percentage of groin lymph node metastases in case of a local recurrence compared to primary SCC is probably explained by earlier diagnosis due to standard follow-up.

2. OBJECTIVES

Primary Objective:

To investigate the safety of replacing complete IFL by SLN procedure in women with a first recurrent vulvar SCC in tumours < 4 cm.

Secondary Objectives:

- 1) To investigate the feasibility of the SLN procedure in patients with a first recurrence of vulvar SCC. (Success rate of the SLN procedure, surgical drawbacks)
- 2) To evaluate the short and long-term morbidity associated with the sentinel lymph node procedure in patients with a first recurrence of vulvar SCC.(complications, wound healing problems, long term sequela, quality of life)
- 3) To evaluate the short and long-term morbidity associated with treatment of a first recurrence of vulvar SCC.(complications, wound healing problems, long term sequela, quality of life)

3. STUDY DESIGN

Preferably a randomized clinical trial or a non-inferiority study should be performed to answer the questions of this study. Given the low incidence of vulvar cancer and the even lower incidence of recurrent vulvar cancer it is not feasible to perform a study other than a multicentre cohort study.

In the participating centres all patients older than 18 years, fit for surgical treatment, with a first vulvar cancer recurrence will be registered.

Standard imaging (i.e., chest, abdominal and groin CT scanning) is performed.

In the absence of distant or proven groin metastases, and when all other eligibility criteria (see Figure 1) are met, the study is proposed and discussed with the patient.

Patients will be informed by oral and written information about the standard treatment (i.e. IFL) and the SLN procedure as part of the study. Patients will be informed that it is possible that the SLN is not traced after injection or at surgery. They will be informed that, should this be the case, standard treatment should be uni- or bilateral IFL. However, from our retrospective study it has become obvious that not all patients will consent for groin treatment and particularly IFL. So three patient groups are identified in *the SLN cohort*. (Figure 1)

- A) Control group: patients who understand the study and choose the standard IFL treatment of the groin(s): These patients will be asked to participate in the conventional treatment arm, with similar questionnaires and follow up.
- B) Patients understanding the study and are willing to undergo a SLN procedure rather than IFL.
 - B1) Patients who agree on IFL(s) in case the SLN is not visible on the lymph scintigram, or not detected at surgery
 - B2) Patients who not agree on IFL(s) in case the SLN is not visible on the lymph scintigram, or not detected at surgery
- C) Patients who agree on vulvar surgery, but refuse any groin surgery. These patients will be asked consent to collect information regarding treatment and outcome, and to fill in the questionnaires.

After surgery *regular follow up* is planned, with visits at 3, 6, 9, 12, 15, 18, 21 and 24 months. For study purposes ultrasonography of the groins is performed at 6 and 12 months. At baseline, at 6 and 12 months QoL questionnaire and a lymph oedema query are requested (see 4.1.3. for questionnaires).

All women with a first vulvar recurrence not eligible for the SLN procedure, unless not capable to read Dutch or English, will be asked to participate in the observational arm of *the non- SLN cohort*. For this purpose a different patient information folder and different consent forms are applicable. They will receive standard (personalised) treatment and follow up. They will be requested to fill in questionnaires at baseline, 6 and 12 months and if they agree on storage and use of any tumour tissues.

[figure not shown]

Figure 1 Flow diagram of patients with a 1st recurrence of vulvar SCC

4. STUDY POPULATION

4.1 Population

In the Netherlands vulvar cancer treatment is centralised in university hospitals and cancer clinics. The annual incidence is rising due to the aging population and due to the increase in HPV related vulvar cancer.[www.iknl.nl] A local recurrence occurs in 20-40% of the women.(13) Although IFL is the standard treatment in local recurrent vulvar cancer, more and more clinics perform a SLN procedure, without data on feasibility and safety. Therefore the willingness of the gynaecologic oncologists to participate in this study is high. However, previous national studies (GROINSS-V and GROINS-VII) have shown that a study like this will take a lot of time. We expect that the willingness of patients to participate in this study will be 80% or above, since they can opt for standard treatment or study treatment rather than being randomized.

4.2 Inclusion criteria

In order to be eligible for the study (non SLN cohort and SLN cohort, group A-C):

- Possible to understand and read Dutch.
- Possible to understand the study and give informed consent.
- No age limit specified.
- Patients should mentally, physically and geographically be able to undergo follow-up.

In order to be eligible to undergo the SLN procedure, a subject must meet all of the following criteria:

- First local recurrent SCC of the vulva.
- Previous treatment with wide local excision or (partial) vulvectomy tumours < 4 cm., not encroaching in urethra, vagina or anus with clinically negative inguinofemoral lymph nodes.
- Localisation and size of the tumour are such that perilesional injection of the tracers at three or four sites is possible.
- Preoperative imaging does not show enlarged (> 10 mm short axis) or suspicious nodes.
- Fit for surgery

4.3 Exclusion criteria

A potential subject who meets any of the following criteria should not undergo the SLN procedure in the study arm (A-B), the patient can be asked for the non SLN cohort.

- Inoperable tumours and tumours with diameter > 4 cm.
- Patients with inguinofemoral lymph nodes at palpation clinically suspect for metastases, at radiology enlarged (> 10 mm short axis) / suspicious groin nodes and with cytological proven inguinofemoral lymph node metastases.
- A history of bilateral IFL **and** radiotherapy to the groins.
- A lateral tumour and history of ipsilateral IFL **and** ipsilateral radiotherapy.
- Tumour encroaching urethra, vagina, or anus.
- Previous surgery of the vulva was not radical (margin < 1 mm) and additional treatment (2nd surgery or radiotherapy) was not performed.
- Multifocal recurrent disease of the vulva.
- Synchronous, non- curable 2nd malignancy.

4.4 Sample size calculation

Approximately 18% of women will have groin metastases at the moment of their first vulvar cancer recurrence. Of these, approximately 20% will be detected prior to surgery (based on imaging and FNA) and these women will not be offered a SLN procedure, but advised to undergo an IFL(s). They will be asked for the observational arm of the non SLN cohort. (See figure 2)

The remaining patients will be informed about the study, they can decide on standard IFL (group A) or refuse any surgery of the groin(s) (group C) In 75% of cases that undergo SLN (group B) it will be possible to retrieve the SLN. In approximately 14,5% of women undergoing a SLN procedure a tumour positive node will be present. It is not expected that the change of a successful SLN procedure relates to the presence or absence of a positive groin node. We expect to find a positive SLN in 11% of cases undergoing a SLN procedure, a negative SLN in 64%, and an unsuccessful procedure in 25%. This corresponds to respectively 10.5%, 61.8% and 24.1% of all included patients.

Percentage failure of SLN or IFL is known for neither procedure in the recurrent setting. In the primary setting groin recurrence after negative IFL and after negative SLN are both about 3%.

Sample size for V2SLN is calculated based on a conservatively estimated groin recurrence rate of 3%, with a maximum additional groin failure rate of SLN in local recurrent vulvar SCC of 5%. The sample size, considering an alpha of 0.10 and a beta of 0.20, is then calculated to be 150 patients with a first vulvar cancer recurrence undergoing a SLN procedure (group B) and a negative SLN (Figure 2) So, we expect that approximately 243 women with a 1st recurrence of vulvar cancer should be included in the study. Stopping rules with dynamic boundaries were constructed to guarantee the safety of the study by continuously monitoring the number of groin recurrences. See Appendix 1 for a detailed description of these stopping rules.

[figure not shown]

Figure 2 Flow diagram of calculation of sample size

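### The forecast of 243 inclusions gives groups A and C a share of zero, so it is a floor and too low as the total needed for 150 negative SLNs

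*Protocol*

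**What the plan says.** Protocol section 4.4 sets the statistical target at "150 patients with a first vulvar cancer recurrence undergoing a SLN procedure (group B) and a negative SLN". It then converts this target into a number to recruit: "So, we expect that approximately 243 women with a 1st recurrence of vulvar cancer should be included in the study".

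The inputs stand in the same section:

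- "Approximately 18% of women will have groin metastases at the moment of their first vulvar cancer recurrence".
- Imaging and FNA are expected to find 20% of these cases preoperatively; the women concerned are not offered SLN and are asked for the non-SLN cohort.
- "In 75% of cases that undergo SLN (group B) it will be possible to retrieve the SLN".
- About 14.5% of women undergoing SLN have a positive node.
- Positive, negative and unsuccessful SLN make up 10.5%, 61.8% and 24.1% of all included patients.

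Of the women left after the preoperative work-up, section 4.4 also says that "they can decide on standard IFL (group A) or refuse any surgery of the groin(s) (group C"). Section 3 adds, from the sponsor's retrospective study, that "not all patients will consent for groin treatment and particularly IFL", and it invites into the non-SLN cohort "All women with a first vulvar recurrence not eligible for the SLN procedure", apart from a language restriction. Section 4.2 sets entry criteria for the study as a whole, covering the non-SLN cohort and groups A to C.

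**The concern.** Only group B women with a retrieved, tumour-negative SLN enter the primary analysis. A total-inclusion figure must therefore allow for every route by which an included woman misses that group. Section 4.4 names two such routes, choosing IFL and refusing groin surgery, but its percentages seem to leave no room for either. The protocol does expect these women: section 1 reports that groin surgery was often omitted in practice, and section 10.2 plans a recurrence rate for group A if enough women choose it.

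If 243 is too low, the recruitment period and feasibility are judged on a favourable figure. Anyone who treats 243 as the point at which recruitment is complete would have fewer than 150 women for the primary analysis.

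**Working it through.** **1. Reproducing 243.**

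- Proven node-positive before surgery: 0.18 x 0.20 = 0.036, leaving 0.964.
- Retrieved and negative among women undergoing SLN: 0.75 x (1 - 0.145) = 0.641.
- Negative SLN among all included: 0.964 x 0.641 = 0.618, the protocol's 61.8%.
- Inclusions: 150/0.618 = 242.7, so 243.

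Deriving the positive share as 0.144/0.964 = 14.9% instead of 14.5% gives 243.9, so that rounding does not matter.

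**2. Is any share left over?** 10.5 + 61.8 + 24.1 = 96.4%, and 96.4 + 3.6 = 100% of included women. Groups A and C have an implicit share of zero. Figure 2 could not be read for this check, but it could not add a further loss without contradicting these printed percentages.

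**3. What 243 does describe.** Women needed in group B: 150/0.641 = 234. Adding 3.6% of 243, about 9 women, gives 243. The figure is correct for group B plus the women found node-positive before surgery, and for nobody else.

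**4. Size of the gap.** Let q be the share of women without preoperatively proven metastases who do not enter group B. Let l be the share of SLN-negative women without 24-month status. The protocol gives neither, so the values below are assumptions.

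- Negative SLNs from 243 inclusions = 243 x 0.618 x (1 - q)
- Inclusions needed = 150/[0.618 x (1 - q) x (1 - l)], rounded up

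| q | Negative SLNs from 243 | Needed, l = 0 | Needed, l = 10% |
|---|---|---|---|
| 0 | 150 | 243 | 270 |
| 10% | 135 | 270 | 300 |
| 20% | 120 | 304 | 338 |
| 30% | 105 | 347 | 386 |

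The last column is a separate matter. Missing 24-month status lowers the evaluable number, not the count of negative SLNs, which is known from pathology after surgery. Section 4.4 makes no allowance for it, although the endpoint runs to 24 months and section 10.3 censors groin recurrence at a further vulvar recurrence.

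**5. Power if recruitment did stop at 243.** Failure rates are 8% against 3%, as in Appendix 1. The calculation is an exact single-stage binomial, with the largest cut-off that keeps one-sided alpha at or below 0.10.

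| SLN-negative women | Most recurrences allowed | Alpha | Power |
|---|---|---|---|
| 150 | 7 | 0.081 | 0.917 |
| 135 | 6 | 0.078 | 0.887 |
| 120 | 5 | 0.075 | 0.847 |
| 105 | 4 | 0.071 | 0.792 |

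Running the printed stopping boundaries at 150 gives alpha 0.0805 and power 0.9160, as in the program output. Against the 0.90 implied by Appendix 1 (beta 0.10), power falls short in all three reduced cases. Against the 0.80 implied by section 4.4 (beta 0.20), it falls short only at 105.

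**The case against.** The strongest defence is that 243 is a forecast and not a recruitment limit. Section 4.4 sets the sample size as 150 women with a negative SLN, the program in Appendix 1 has a maximum of 150, and section 12.5 ends the study on a count of treated women. No section closes recruitment at 243. This stands. A reader might infer that the trial cannot reach 150, or that its alpha and power are lost, but the documents do not support that. The entry of not applicable in section 8.5 on replacement does not bar recruiting on either.

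A reader might also keep the limit of 7 recurrences with fewer women, which would give alpha of 0.146, 0.247 and 0.391 at 135, 120 and 105. Nothing in the protocol prescribes that limit at a smaller number, so these values do not describe the plan.

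Women ineligible for SLN for other reasons (for example large or multifocal tumours) may lie outside the 243. Section 13.2 and Appendix 6 set the non-SLN cohort apart from V2SLN, and section 4.4 labels its calculation as one for V2SLN. Yet the 3.6% found node-positive before surgery also go to the non-SLN cohort and are counted. The text is ambiguous, so this part of the point is conditional. The part on groups A and C is not, because both belong to V2SLN.

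The expected willingness of 80% or above in section 4.1 does not fill the gap. It is willingness to take part with either treatment, not uptake of SLN.

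**Conclusion.** The point holds as one about the inclusion forecast. The figure of 243 is reproduced exactly and leaves a zero share for groups A and C, which the same section allows. Every omitted loss acts in the same direction, so 243 is a floor and too low as a total-inclusion figure.

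The size of the gap cannot be fixed from the protocol. It rests on the assumed values of 10 to 30% for women not entering group B and 10% for missing 24-month status. Over that range the need is about 270 to 347 inclusions, or 300 to 386 with the loss. Women ineligible for other reasons add to the assumed share only if they count among the 243. The statistical target of 150 stands, and loss of power is a consequence only of stopping near 243.

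**What to change.** 1. Relabel 243 as the women entering the SLN strategy (group B, about 234) plus the 3.6% found node-positive before surgery (about 9).
2. Give expected total inclusions as 150/[0.618 x (1 - share not entering group B) x (1 - loss)], with the assumed shares stated and a range shown. Say whether the total includes women in the non-SLN cohort who are ineligible for other reasons.
3. State that recruitment ends on 150 group B women with a negative SLN and evaluable 24-month status, not on total inclusions.
4. Reconcile this with the 125 successfully treated patients in section 12.5, and reconcile the two betas (0.20 in section 4.4, 0.10 in Appendix 1).

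The cost is a larger and less favourable inclusion forecast, with the longer recruitment that it implies. The target of 150 does not change.
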